3.3 Exclusion Criteria

3.3.1 Patients currently receiving anticancer therapies or who have received anticancer therapies within 4 weeks of the start of the investigational therapy (including chemotherapy, radiation therapy, antibody based therapy).

3.3.2 Her2/neu positive¹⁰² or estrogen and progesterone receptor negative¹⁰¹ breast cancer. Patients with triple-negative breast cancer are also excluded.

3.3.3 Metastatic breast cancer.

3.3.4 Inflammatory (T4d) breast cancer.

3.3.5 Patients may not be receiving any other investigational agents. If patients are currently part of or have participated in any clinical investigation with an investigational drug, the last administration of the investigational study should be at least 1 month prior to dosing.

3.3.6 Inoperable breast cancer even after neoadjuvant treatment as assessed by the treating surgical oncologist.

3.3.7 Undetermined or unknown menopausal status.

3.3.8 Disease that cannot be measured and/or accurately followed by mammogram and/or breast ultrasound and/or dedicated breast MRI.

3.3.9 Target lesion that has been previously irradiated.

3.3.10 History of allergic reactions, intolerance or hypersensitivity attributed to compounds of similar chemical or biologic composition to TRC105 and/or everolimus or other rapamycin analogs (e.g. sirolimus, temsirolimus).

3.3.11 Known impairment of gastrointestinal (GI) function or GI disease that may significantly alter the absorption of oral Everolimus

3.3.12 Patients must have normal organ and marrow function. Patients with any of the following abnormal parameters will be excluded:

- leukocytes <3,000/mcL
- absolute neutrophil count <1,500/mcL
- hemoglobin <10 gr/dL
- platelets <100,000/mcL

- total bilirubin >2 X institutional ULN (except for known Gilbert's syndrome/familial non-hemolytic jaundice)
- AST(SGOT)/ALT(SGPT) >2.5 X institutional upper limit of normal
- creatinine > 1.5 UNL, or
- creatinine clearance <40 mL/min/1.73 m² for patients with creatinine levels above institutional normal.
- INR ≥2

3.3.13 Uncontrolled diabetes mellitus as defined by HbA1c >8% despite adequate therapy. Patients with a known history of impaired fasting glucose or diabetes mellitus (DM) may be included, however blood glucose and antidiabetic treatment must be monitored closely throughout the trial and adjusted as necessary.

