4.1.1 Definition of a Dose Limiting Toxicity (DLT)

A **dose-limiting toxicity (DLT)** is defined as:

- a) Any grade 3 or 4 non-hematologic toxicity except anorexia, alopecia, nausea (which is not refractory to antiemetics), fatigue, fever without neutropenia;
 - b) Failure to recover to baseline (except alopecia) after delaying the next dose by more than 14 days;
 - c) Grade 3 or 4 neutropenia complicated by fever >38.5°C or infection, or grade 4 neutropenia of ≥7 days duration; or
 - d) Grade 4 thrombocytopenia, or grade 3 thrombocytopenia complicated by hemorrhage.
- In addition, accrual will be halted as a result of any grade ≥3 hemorrhage, cerebrovascular and vasovagal adverse events; FDA will be contacted to discuss further accrual or potential need for protocol amendment.

4.1.2 Dose escalation rule:

Dose escalation will follow the decision rules shown in **table 4-2**.

Table 4-2. Dose escalation rules

Number of Patients with DLT at a Given Dose Level	Escalation Decision Rule
0 out of 3	Enter 3 patients at the next dose level.
1 out of 3	Enter 3 additional patients in the same dose level (for a total of 6 patients at this dose level). If 0 of the 3 additional patients experience DLT, then proceed to the next dose level. If 1 or more of these additional patients experience DLT (i.e., ≥ 2 of 6 total patients), dose escalation will be

	stopped.
≥ 2 out 3	Dose escalation will be stopped.
If MTD not reached	Cohort 2 will be selected for RP2D

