4.1.3 Definition of Maximum Tolerated Dose (MTD)

The **maximum tolerated dose** (MTD) is defined as the highest dose at which 0 out of first 3 or 1 out of total of 6 patients experience DLT during the first cycle of therapy; this dose level will be recommended as RP2D in the second portion of the study. If accrual to cohort 2 (highest dose of both everolimus and TRC105) is completed without reaching the MTD, this dose will be selected as the RP2D. In every cohort, patients withdrawn without receiving study treatment will be replaced, as will patients withdrawn before completing the first cycle of treatment for any reason other than DLT.

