4.3 Study accrual and treatment considerations

It is anticipated that 26 – 38 patients will be enrolled in the study and accrual is expected to be completed in 24 months (see Section **10. STATISTICAL CONSIDERATIONS**). Patients meeting the eligibility criteria and who have signed the consent form will start Letrozole 2.5 mg PO daily, Everolimus 5 or 10 mg PO daily, and TRC105 15 or 10 mg/kg IV every two weeks with the first infusion administered in 2 split doses on days 1 (3 mg/kg) and 4 (12 mg/kg or 7 mg/kg), respectively. Premenopausal women at the time of study enrollment will receive goserelin 3.6 mg subcutaneously q 4 weeks to achieve ovarian suppression. A cycle is defined as 4 weeks of treatment. Breast ultrasound, will be conducted upon completion of each cycle to complement clinical assessments of the size of the tumor(s). The duration of neoadjuvant therapy is 24 weeks or 6 cycles. No extensions of the neoadjuvant therapy beyond 6 months are allowed. After neoadjuvant therapy, patients will undergo surgical treatment and will receive adjuvant therapy (radiation therapy, chemotherapy, hormonal therapy) according to the standard of care or at the discretion of the treating physician. The accrual rate is projected to be approximately 1-2 patients per month. Accrual will be halted as a result of any grade ≥ 3 hemorrhage, cerebrovascular and vasovagal adverse events; FDA will be contacted to discuss further accrual or potential need for protocol amendment.

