Adverse events. The addition of everolimus to letrozole has been associated with a higher rate of dose reductions or interruptions due to adverse events (52.9%) as well as discontinuations (18.8%) compared with letrozole alone (7.6% and 9.1%, respectively) in the neoadjuvant setting⁴. Grade 1 and 2 adverse events were also more frequent in the combination arm (89.8% vs. 63.6% in the letrozole alone arm)⁴. The most frequent adverse events seen in higher frequency in the combination arm as compared to the letrozole alone group include stomatitis (36.5% vs. 6.1%), rash (20.4% vs. 7.6%), asthenia (17.5% vs. 9.8%), fatigue (12.4% vs. 4.5%), anorexia (12.4% vs. 3.8%), headache (10.9% vs. 5.3%), pruritus (13.1% vs. none), dyspnea (7.3% vs. 1.5%), pneumonitis (2.9% vs. none). Laboratory abnormalities seen in higher frequency in the combination arm as compared with the control arm include hypercholesterolemia (16.1% vs. 6.1%), thrombocytopenia (18.2% vs. 0.8%), hyperglycemia (13.1% vs. 3%), increased ALT (11.7% vs. 3.8%), anemia (11.7% vs 0.8%), and neutropenia (9.5% vs. 1.5%).

Grade 3 and 4 adverse events were also more frequent in the combination arm (22.6%) as opposed to the letrozole alone arm (3.8%). Stomatitis (2.2%), fatigue (1.5%), and pneumonitis (2.2%) were the most frequent grade 3 and 4 adverse events seen in more than 1 patients (n=137) associated with the addition of everolimus, while hyperglycemia (5.1%), increased ALT (1.5%), hypokalemia (1.5%), thrombocytopenia (1.5%) constituted the most frequent biochemical grade 3 and 4 adverse events. Serious adverse events associated with everolimus occurred in 7/137 patients: pneumonitis in three patients; pneumonia and mouth ulcers/stomatitis each in two patients; and dyspnea, neutropenia, and thrombocytopenia in one patient each. All three patient cases of pneumonitis resolved within 15 days of everolimus discontinuation. Among the placebo-treated patients, there was one serious adverse event of myocardial ischemia⁴.

Overall, safety data available from completed, controlled and uncontrolled studies indicate that everolimus is generally well tolerated at weekly or daily dose schedules. The safety profile is characterized by manageable adverse events (AEs). These AEs are generally reversible and non-cumulative.

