5.4.2 Treatment Phase

The following evaluations and procedures will be performed during the **treatment phase**: (All assessments should be performed within 5 working days of the protocol-specified date).

- Physical examination, vital signs, weight, and performance status on weeks 4, 8, 12, 16, 20 and 24.
- Laboratory assessments: CBC with differential and platelet count, serum chemistries (glucose, BUN, creatinine, total protein, albumin, bilirubin, calcium, alkaline phosphatase, AST, and ALT), and serum electrolytes (Na, K, Cl) on week 1 and at the beginning of each cycle until week 24.
- Lipid panel (cholesterol, triglycerides, HDL, and LDL) in a fasting state (at least 8 hours) should be obtained at least on cycle 2 and, if elevated, repeated on each cycle until recovery to baseline value or grade 1 (see 5.2.2.2 for management of hyperlipidemia and hyperglycemia).

Serum estradiol levels on weeks 4, 12, and 20 in women receiving goserelin.

- Hepatitis panel as clinically indicated.
- Research biopsy (core needle biopsy of the tumor) at week 4 (required).
- Tumor assessments: Ultrasound of the breast will be obtained on week 4, 8, 12, 16, 20 and 24. Mammogram will be obtained on week 24. Additional PET scans or CT of the chest, abdomen, and pelvis, or bone scans are not required during treatment phase except as clinically indicated (see section **7.2 Measurement of Effect**). MRI breast will be obtained at baseline, week 12 and 24.
- Evaluation of the ejection fraction with an echocardiogram/MUGA only as clinically indicated.
- Surgical evaluation at the end of neoadjuvant therapy. **There must be at least 4 weeks between the last dose of everolimus and TRC105 and surgery.** Patients will continue letrozole until the day before surgery.
- Concomitant medication assessment.
- Assessment of adverse events.

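### No CBC or chemistry is required between week 1 (C1D4) and C2D1, so short silent laboratory DLTs can go unseen in the cycle that sets the MTD; one draw at C1D15 is a cheap, minor improvement

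*Combined protocol and SAP*

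**What the plan says.** Section 5.4.2 schedules CBC with differential and platelets, serum chemistries and "serum electrolytes (Na, K, Cl) on week 1 and at the beginning of each cycle until week 24". In Table 7-1 the CBC and chemistry rows are marked at screening, C1D4, C2D1 and day 1 of each later cycle; C1D15 is blank. Text and table therefore agree.

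Section 4.3 fixes the time scale: "A cycle is defined as 4 weeks of treatment". Section 4.1.3 defines the MTD by how many "patients experience DLT during the first cycle of therapy". Section 4.1.1 counts as DLTs several findings that only a blood test may reveal: "Grade 4 thrombocytopenia, or grade 3 thrombocytopenia complicated by hemorrhage", neutropenia with fever or infection "or grade 4 neutropenia of ≥7 days duration; or" and any grade 3-4 non-hematologic toxicity outside a short list of exceptions that does not include chemistry values.

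TRC105 is infused at C1D15 (section 6.1.3), and serum is drawn that day for angiogenesis markers (section 7.3.2). Examination is not planned then: section 5.4.2 lists "Physical examination, vital signs, weight, and performance status on weeks 4, 8, 12, 16, 20 and 24", and Table 7-1 marks it at C1D1 and C2D1.

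Other monitoring text gives no day. For patients with diabetes or impaired fasting glucose, "blood glucose and antidiabetic treatment must be monitored closely throughout the trial" (section 3.3.13). Sections 5.2.2.2, 5.2.2.7 and 8.3.1 advise monitoring of glucose, renal function and anemia. Section 7.1 repeats laboratory tests only if the patient is deteriorating, and ties them to the start of the next cycle.

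**The concern.** A laboratory DLT that begins after the week 1 draw and resolves before C2D1 leaves no trace in the required data. The error runs one way: an unseen DLT can only lower the count, and so can only favour clearing a dose.

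The dosing rules meet the same gap. Table 5-3 interrupts everolimus for grade 3-4 platelets, neutrophils or anemia, and some restart rules turn on whether recovery took 7 days or less. Section 5.2.3.3 lowers TRC105 from 15 to 10 mg/kg for grade 3 or higher anemia. At C1D15, halfway through the first cycle of a combination not given before (section 4.4), no result is required on which to apply either rule.

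**Working it through.** The plan states no figure on this point, so there is none to reproduce. The check is of the calendar, followed by an illustration.

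**Calendar**
- Required draws fall on day 4 (Table 7-1) and day 29 (C2D1). The gap is 29 − 4 = 25 days, or 29 − 8 = 21 if week 1 is read as day 8.
- Section 7.1 allows ±3 days, so the draws fall no later than day 7 and no earlier than day 26. Section 5.4.2 allows 5 working days, about 7 calendar days, which gives day 11 and day 22. Neither window moves a draw from its Table 7-1 date to day 15. Only the day-8 reading with the whole looser window just reaches it (8 + 7 = 15), and then it is allowed, not required.
- Showing 7 days of grade 4 neutropenia from scheduled draws alone needs an episode covering both day 4 and day 29, which is 26 days.

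**Share of episodes seen.** Assumption: onset is equally likely on each of days 5 to 28 (24 days) and the abnormality lasts L days.
- Day 29 alone: onsets 23-28 for L = 7 (6/24), 16-28 for L = 14 (13/24), 9-28 for L = 21 (20/24).
- Days 15 and 29: L = 7 gains onsets 9-15 (13/24); L = 14 gains 5-15 (24/24); L = 21 gains 5-8 (24/24).
- If both draws move within ±3 days, the 7-day share ranges from 10/24 to 14/24 and the 14-day share from 18/24 to 24/24.

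**Laboratory-DLT rate.** Section 5.2.2 gives grade 3-4 rates for everolimus plus letrozole in the 4-month neoadjuvant trial: hyperglycemia 5.1%, ALT 1.5%, hypokalemia 1.5%, thrombocytopenia 1.5%. Spread evenly over four cycles:
- all four: 9.6/4 = 2.4%
- without glucose: 4.5/4 = 1.1%
- ALT and hypokalemia only: 3.0/4 = 0.75%

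The first two count grade 3 platelets, which are a DLT only with hemorrhage. All three assume that no patient has two events.

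**3+3 rule.** A dose clears with 0/3 DLTs, or with 1/3 followed by 0/3:

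C = (1 − p)³ + 3p(1 − p)⁵, where p = 1 − (1 − other)(1 − f × lab) and f is the share seen.

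With other = 15% (assumed) and lab = 2.4%, full detection gives p = 1 − 0.85 × 0.976 = 0.170 and C = 77.2%. For 7-day episodes under the current schedule, p = 1 − 0.85 × (1 − 0.25 × 0.024) = 0.155 and C = 80.3%.

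| Episode | Seen now | Seen with C1D15 | C now | C with C1D15 | Drop (points) |
|---|---|---|---|---|---|
| 7 days | 25% | 54% | 80.3% | 79.1% | 1.2 |
| 14 days | 54% | 100% | 79.1% | 77.2% | 1.9 |
| 21 days | 83% | 100% | 77.9% | 77.2% | 0.7 |

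The present excess over full detection is 3.2, 1.9 and 0.7 points. For 7-day episodes 1.9 points remain after the fix; subtracting those rounded figures gives 1.3, while the unrounded drop is 1.2.

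The same formula gives these drops for 7-, 14- and 21-day episodes:
- lab 1.1%, other 15%: 0.6, 0.9, 0.3
- lab 0.75%, other 15%: 0.4, 0.6, 0.2
- lab 2.4%, other 5%: 0.8, 1.3, 0.5
- lab 2.4%, other 25%: 1.1, 1.8, 0.6

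**The case against.** The case on the other side is that this is a preference about monitoring frequency. C1D15 is an attended infusion visit, Table 7-1 runs adverse-event assessment throughout, investigators may order tests, and an abnormality that persists is caught at C2D1. Phase II goes on evaluating safety in up to 20 patients at the RP2D, so a dose cleared too easily would still be examined. The illustration rests on assumed rates, and one draw leaves most of the excess for 7-day episodes in place. All of this stands, and it keeps the point minor. It does not supply a required result for a silent abnormality.

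Several stronger readings are tempting, and the documents do not support them:
- **The hemorrhage at 60,000/µL shows why a count is needed before the infusion.** Table 5-3 treats that count as grade 2 with no action, and section 5.3.3 sets no platelet threshold for TRC105. Section 8.3.3 explains that the hepatocellular protocol admitted patients at that level; this trial requires 100,000 at entry.
- **Thrombocytopenia is common enough to make the gap serious.** The 18.2% in section 5.2.2 is any grade over 4 months. The grade 3-4 rate, which triggers action, is 1.5%.
- **C1D15 is the first exposure to the full dose.** The split dose already totals 3 + 12 = 15 mg/kg by day 4, and section 5.2.3.1 splits it to limit infusion reactions.
- **Anemia DLTs are being missed.** Anemia is not among the hematologic DLTs in section 4.1.1. Here it bears only on dosing.

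**Conclusion.** The point holds as a minor one. The calendar facts are firm: text and table agree, and no other dated requirement closes the gap. The consequence is limited to silent laboratory abnormalities that resolve before C2D1, and to dosing rules without a required result at C1D15.

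A reader might infer that the MTD is unreliable. The figures do not show that. With other DLTs at 15%, the draw changes the chance of clearing a dose by 0.2 to 1.9 points across the three rates and three durations. These sizes rest on uniform onset, equal risk in each cycle and rates observed without TRC105. The documents give no cycle-1 laboratory-DLT rate or episode duration for this combination, so 2.4% is not a ceiling; early clustering or added TRC105 toxicity would raise it. For episodes that last to C2D1 the effect is zero.

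**What to change.** In section 5.4.2 and Table 7-1, add CBC with differential and platelets plus the chemistry/electrolyte panel at C1D15, drawn at the existing venipuncture and reviewed before the infusion. Require a repeat count after any grade 4 neutropenia so that its 7-day duration can be judged; a single draw cannot establish it.

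The cost is a calendar amendment, one or two routine tubes and a short wait for results, with no new routine visit (a repeat count after grade 4 neutropenia may need one). The longest planned gap falls from 25 to 14 days (29 − 15), or up to 20 if the draws move 3 days apart in opposite directions (32 − 12). Episodes shorter than the gap can still be missed: about 46% of 7-day episodes (11/24) on the nominal days. Day 15 of cycles 2-6 lies outside the DLT window, so a CBC there is optional.

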Following the appropriate premedication regimen, the patient will receive TRC105 on day 1 and day 15 of every cycle. The first TRC105 dose will be split with 3 mg/kg administered on cycle 1 day 1 and infused over 4 hours (+/- 15 minutes) and 12 mg/kg (or 7 mg/kg if dose is de-escalated) administered on cycle 1 day 4 and infused over 2 hours (+/- 15 minutes), and then the full dose of 15 mg/kg (or 10 mg/kg if dose is de-escalated) given on cycle 1 day 15 and every 2 weeks thereafter and will be administered over a minimum of 90 minutes. The patient must complete at least one 4 hour infusion (+/- 15 minutes) without the development of any infusion reactions, in order to reduce the subsequent TRC105 infusion to 2 hours (+/- 15 minutes) and complete a 2 hour infusion (+/- 15 minutes) without the development of any infusion reactions in order to reduce subsequent TRC105 infusions to a **minimum of 90 minutes**. If the patient develops infusion reactions of any kind they should be managed appropriately (see [Section 5.3.2.1](#)) and the patient is not permitted to reduce the duration of the next planned infusion.

The rate of TRC105 infusion must not exceed 25 mg/min. When the i.v. bag containing TRC105 is empty, flush the i.v. line with a 20 mL normal saline. The dose level, time of transfer to i.v. bag, and the infusion start and stop times must be recorded in the source documents.

If the patient misses a TRC105 dose (i.e., ≥ 18 days between doses), the full premedication (including methylprednisolone) should be reinstated as per the initial infusion and TRC105 dose should be administered over two days as was done for the initial dose.

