6.2.4 Goserelin Formulation

Goserelin is supplied as a sterile, biodegradable product containing goserelin acetate equivalent to 3.6 mg of goserelin. Goserelin is designed for subcutaneous injection with continuous release over a 28-day period. Goserelin acetate is dispersed in a matrix of D,L-lactic and glycolic acids copolymer (13.3-14.3 mg/dose) containing less than 2.5% acetic acid and up to 12% goserelin-related substances and presented as a sterile, white to cream colored 1-mm diameter cylinder, preloaded in a special single use syringe with a 16-gauge x 36 +/- 0.5 mm siliconized needle with protective needle sleeve (SafeSystem™ Syringe) in a sealed, light and moisture proof, aluminum foil laminate pouch containing a desiccant capsule. Studies of the D,L-lactic and glycolic acids copolymer have indicated that it is completely biodegradable and has no demonstrable antigenic potential (AstraZeneca, Package Insert).

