7. VISIT SCHEDULE AND ASSESSMENTS

7.1 Study Flow and Visit Schedule

Figure F and **table 7-1** (following page) list all the assessments and indicate with an “x” the times they need to be performed.

Baseline evaluations are to be conducted within 1 week prior to start of protocol therapy. Imaging studies must be done within 4 weeks prior to the start of therapy. In the event that the patient's condition is deteriorating, laboratory evaluations should be repeated within 48 hours prior to initiation of the next cycle of therapy. For all visits except day 1, there is a temporal window of ± 3 days to account for holidays, inclement weather or other extraneous circumstances. The temporal window does not apply for PK sampling, which needs to be undertaken at the specified time frames. Every effort must be undertaken to follow this schedule.

In patients who discontinue their treatment early, all procedures outlined in 5.4.3 (5.4.3 **Safety Follow-up Phase**) must occur within 10 days. Patients who complete the protocol treatment and proceed to surgery as planned do not need to have an end of treatment visit.

Premenopausal women at the time of study enrollment will receive goserelin 3.6 mg subcutaneously q 4 weeks to achieve ovarian suppression.

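### Table 7-1 stops goserelin at C6D1 although the text gives it every 28 days with no stop date; if C6D15 TRC105 and the 4-week interval before surgery are kept, at least 14 letrozole days have no scheduled depot

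*Combined protocol and SAP*

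**What the plan says.** Letrozole and surgery (5.4.2): "Patients will continue letrozole until the day before surgery". For the other two agents, "There must be at least 4 weeks between the last dose of everolimus and TRC105 and surgery".

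TRC105 (6.1.3): "the patient will receive TRC105 on day 1 and day 15 of every cycle". With the six cycles in 4.3, the last infusion is C6D15.

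Goserelin: the synopsis, 4.1, 4.3, 7.1 and Table 6-1 give 3.6 mg every 4 weeks. Section 5.2.4 says every 28 days, and 5.3.4 limits delay to 3 days. None of these gives a stop date. On duration of action, 6.2.4 says: "Goserelin is designed for subcutaneous injection with continuous release over a 28-day period". The goserelin row of Table 7-1 has six marks, C1D1 through C6D1, and none at C6D15, end of treatment or follow-up.

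Visits and monitoring: 5.4.2 lists "Physical examination, vital signs, weight, and performance status on weeks 4, 8, 12, 16, 20 and 24" and "Serum estradiol levels on weeks 4, 12, and 20 in women receiving goserelin". Section 7.1 adds: "Patients who complete the protocol treatment and proceed to surgery as planned do not need to have an end of treatment visit".

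Duration (4.3): 24 weeks or six cycles, with no extension past 6 months.

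**The concern.** Sections 2.1.10 and 4.4 hold that a premenopausal woman must be made postmenopausal before she can receive an aromatase inhibitor. Goserelin cover should therefore last as long as letrozole does. The text implies that it will; the calendar, which sites use to book visits and doses, stops one depot earlier.

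The visit at which the missing dose would fall due is itself uncertain. Section 5.4.2 has a week-24 examination, but in Table 7-1 week 24 is the end-of-treatment column, and 7.1 excuses that visit for women who go to surgery as planned. Section 5.6 makes estradiol in the premenopausal range a reason to discontinue, yet no estradiol is scheduled after week 20.

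At stake is whether premenopausal women are protected in the last weeks before surgery. The estimate of the MTD is not at issue.

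**Working it through.** Convention: C1D1 is day 1, and day = (cycle − 1) × 28 + cycle day.

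**Check against the plan's own figures.** 6 × 28 = 168 days = 24 weeks, as in 4.3. The estradiol visits C2D1, C4D1 and C6D1 are days 29, 85 and 141. (29 − 1)/7 = 4, (85 − 1)/7 = 12 and (141 − 1)/7 = 20 weeks, as in 5.4.2. Week 24 is therefore day 169. The ultrasound and MRI rows place it in the end-of-treatment column.

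**Goserelin cover.** The last marked depot is C6D1, day 141. With 28-day release, cover runs through 141 + 27 = day 168, and the next depot is due on day 169.

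**Letrozole end.** The last TRC105 is C6D15 = 5 × 28 + 15 = day 155. Earliest surgery is 155 + 28 = day 183, so letrozole runs to day 182. This rests on 6.1.3, because the TRC105 row of the table prints one mark more than there are dosing columns.

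**Gap.** 182 − 168 = 14 days (169 to 182). It is a minimum for on-schedule dosing, since the interval to surgery may exceed 4 weeks.

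**Dosing windows.**
- Goserelin 3 days late (day 144, cover to 171) and TRC105 3 days early (day 152, surgery 180, letrozole to 179): 179 − 171 = 8 days.
- Goserelin on time and TRC105 3 days late (day 158, surgery 186, letrozole to 185): 185 − 168 = 17 days.
- If the last goserelin may also be given 3 days early (day 138, cover to 165): 185 − 165 = 20 days. Section 5.3.4 speaks only of delays, so 8 to 17 days is the range it supports.

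**Other readings of the surgery date.**

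| Reading | Surgery | Last letrozole day | Gap | What it conflicts with |
|---|---|---|---|---|
| C6D15 kept, 4-week rule kept | day 183 | 182 | 14 days | 182/7 = 26 weeks, against 24 in 4.3 |
| Last TRC105 on C6D1, surgery at week 24 | day 169 | 168 | 0 | drops the C6D15 infusion in 6.1.3 |
| C6D15 kept, surgery within a week of day-169 imaging | days 169–176 | 168–175 | 0–7 days | only 14–21 days after TRC105 |
| Everolimus through day 168, 4-week rule kept | day 196 | 195 | 27 days | 195/30.4 = 6.4 months, against the 6-month cap |

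**Note 7 of Table 7-1.** It puts the end-of-treatment assessments within a week of surgery. Section 5.4.2 allows: "All assessments should be performed within 5 working days of the protocol-specified date". Five working days after day 169 is day 176, and 176 + 7 = 183. With on-schedule C6D15 TRC105, note 7 and the 4-week rule can therefore both hold only on day 183. Under the 3-day visit window of 7.1, imaging is by day 172 and surgery by 172 + 7 = 179, before 183, so no date satisfies both.

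**Monitoring.** The last scheduled estradiol is on day 141: 183 − 141 = 42 days before the earliest surgery in the first row.

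**With a seventh depot.** A dose on day 169 covers through 169 + 27 = day 196, and so any surgery through day 197. That closes both the 14-day and the 27-day case.

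**The case against.** The strongest reply is that the text already requires the seventh dose. The 4-weekly schedule is repeated throughout, including in 7.1 where the calendar is introduced; no stop date is given; and the stated purpose of goserelin implies dosing for as long as letrozole is taken. On this view the calendar has one blank cell and a careful site would fill it. That is a fair account of the intent, and it makes this a conflict to clear up rather than a decision to stop suppression early. It does not remove the conflict, because the calendar omits the dose and 7.1 excuses the visit where it would be given.

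The second reply is that the trial is a 24-week treatment. The surgery mark in Table 7-1, as extracted, sits in the same column as the week-24 mammogram. If everything ends at week 24, six depots cover exactly through day 168 and there is no gap. This also stands as a reading, but it requires either omitting C6D15 TRC105 or operating 14 to 21 days after it, and each breaks an explicit rule.

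Third, 5.6 already allows discontinuation for premenopausal-range estradiol at any time on treatment. The criterion exists, but no scheduled sample tests it after week 20.

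**Conclusion.** The conflict between Table 7-1 and the dosing text is real. Provided that C6D15 TRC105 is given, the 4-week interval is kept and a site follows the calendar for goserelin, at least 14 letrozole days have no scheduled depot when doses are on time. Shifting doses within their windows moves this minimum to between 8 and 17 days. Surgery at week 24 makes it zero, at the price of another rule. The underlying cause is that the documents never reconcile the surgery date with C6D15, the 4-week interval and the 24-week duration.

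A reader might infer that these women will lose ovarian suppression, or that pCR, downstaging or surgical Ki67 will be distorted. The documents do not support that. They give a 28-day release period but do not say how fast suppression fades afterwards. The figure in 5.2.4 of isolated estradiol rises in up to 10% of patients concerns women after suppression was attained; it supports a late check but is not a failure rate after a missed depot. Nor do the documents say how many women will be on goserelin. The primary endpoint (MTD, RP2D and adverse-event rates) is unaffected. This is a small safety correction, worth making because it costs so little.

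**What to change.** 1. State in 5.2.4 and Table 7-1 that goserelin continues every 28 days until letrozole stops.
2. Mark a dose on day 169 (week 24), and say in 7.1 that this visit is required for women on goserelin who are still awaiting surgery.
3. Draw serum estradiol at that visit, so that the 5.6 criterion is tested after week 20 while there is still time to act. A second sample could be added to the pre-surgery serum draw already in 7.3.2, but taken alone it would find a lapse too late to correct it.
4. State once that surgery is at least 28 days after C6D15 TRC105, with letrozole and goserelin continuing past week 24 until then. Bring the 24-week duration in 4.3, the last everolimus day and note 7 into line with this; for surgery on day 183, everolimus must stop by day 155.

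The cost is one depot and one estradiol assay per woman on goserelin, a week-24 visit that 7.1 might otherwise have excused, and wording edits. A further depot is needed only if surgery falls after day 197. Sample size and analyses do not change.
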